9.7.1.1.2 SECONDARY ENDPOINTS

The key secondary endpoints of the study are as follows (revised per Amendment 05):

- Change from baseline in ADCOMS at 24 months in the combined studies
- Change from baseline in amyloid PET SUVR at 24 months for brain amyloid levels in the combined studies
- Change from baseline in amyloid PET SUVR at 24 months for brain amyloid levels in the individual studies

The other secondary endpoints of the study are as follows (revised per Amendment 05):

- Change from baseline in the CDR-SB at 24 months for subjects enriched by baseline PET SUVR, eg, between 1.2 and 1.6, in the combined studies
- Change from baseline in the ADCOMS at 24 months for subjects enriched by baseline PET SUVR, eg, between 1.2 and 1.6, in the combined studies
- The rate of change over time (mean slope) based on CDR-SB score over 24 months in the combined studies
- Time to worsening of CDR scores by 24 months (eg, the worsening of global CDR score is defined as an increase from baseline by at least 0.5 points on the global CDR scale on 2 consecutive scheduled visits at which global CDR is undertaken) in the combined studies

- Time to conversion to dementia by 24 months for subjects who were not clinically staged as dementia at Baseline based on clinical diagnosis in the combined studies
- Change from baseline in CDR-SB at 27 months (ie, 24 months of treatment plus 3 months posttreatment follow-up) in the combined studies
- Change from baseline in ADAS-cog14, MMSE, and FAQ at 24 months in the combined studies
- Change from baseline in ADAS-cog14 Word List (immediate recall and delayed recall) at 24 months in the combined studies

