9.7.1.2 Definitions of Analysis Sets

- The Randomized Set is the group of subjects who are randomized to study drug.

- The Safety Analysis Set is the group of subjects who receive at least 1 dose of study drug and have at least 1 postdose safety assessment.
- The Full Analysis Set (FAS) is the group of randomized subjects who receive at least 1 dose of study drug and have baseline and at least 1 postdose primary efficacy measurement.
- The Per Protocol Analysis Set (PPS) is the subset of subjects in the FAS who sufficiently comply with the protocol. The PP Analysis Set will be used to conduct a sensitivity analysis of the primary efficacy endpoint. Details of the evaluability criteria will be determined before database lock and treatment unblinding, and will be specified in the statistical analysis plan.
- The PK Analysis Set is the group of subjects with at least 1 quantifiable elenbecestat plasma concentration with a documented dosing history.
- The PD Analysis Set is the group of subjects who have sufficient PD data to derive at least 1 PD parameter.

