9.7.1.6.1 PRIMARY EFFICACY ANALYSIS

The primary analysis will be based on an intent to treat philosophy without regard to adherence to treatment. The primary analysis of the change from baseline in CDR-SB at 24 months will be performed to compare elenbecestat 50 mg per day versus placebo using a linear mixed effects model for repeated measures (MMRM) on the FAS. The MMRM model will include fixed effects of treatment group, visit, treatment group by visit interaction, baseline CDR-SB, baseline CDR-SB by visit interaction, and randomization stratification variables (ie, region [7 levels], clinical dementia [yes, no], and concurrent AD medication use at randomization [Visit 2] [yes, no]). *ApoE4* status may be included in the model if appropriate. (revised per Amendment 05) An unstructured covariance matrix will be employed to model the covariance of within subject effect; if MMRM fails to converge then a covariance structure with fewer parameters from the following list will be employed according to the prespecified order in the list until the MMRM converges. The list of covariance structure will include Heterogeneous Toeplitz, Toeplitz, Heterogeneous Compound Symmetry, and Compound Symmetry. This primary analysis will include all observed post baseline data of the change from baseline in CDR-SB without imputation of missing values. The treatment effect for elenbecestat versus placebo will be compared at

24 months based on MMRM model. The LS means and difference in LS means between elenbecestat treatment group and placebo, and corresponding 95% CI will be presented.

The null hypothesis is that there is no difference in the mean change from baseline in CDR-SB at 24 months between elenbecestat 50 mg per day and placebo. The corresponding alternative hypothesis is that there is a difference in the mean change from baseline in CDR-SB at 24 months between elenbecestat 50 mg per day and placebo.

The primary analysis will be repeated to minimize the impact of change in concomitant AD medications where efficacy data after initiation of new AD medications and increase of current AD medications will be censored.

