9.7.1.6.2 SECONDARY EFFICACY ANALYSES

Analyses for Key Secondary Efficacy Endpoints (revised per Amendment 05):

The key secondary analyses will be performed only if the primary analysis is significant. The treatment effect for elenbecestat 50 mg/day versus placebo, for each key secondary efficacy endpoint, will be tested using a sequential testing procedure at a significance level of 2-sided $\alpha = 0.05$, ie, any test will start only if the test with higher hierarchical order is significant.

The change from baseline in ADCOMS at 24 months will be analyzed using the same MMRM model as the primary efficacy analysis to compare elenbecestat 50 mg per day versus placebo on the FAS, using baseline ADCOMS in the model.

The change from baseline in amyloid PET SUVR at 24 months will be analyzed using the same MMRM model as the primary efficacy analysis to compare elenbecestat 50 mg per day versus placebo on the FAS, using baseline amyloid PET SUVR in the model. The same analysis will be performed within study as key secondary efficacy endpoint analyses.

Analyses for Other Secondary Endpoints (revised per Amendment 05)

The change from baseline in CDR-SB and ADCOMS at 24 months will be analyzed using the same MMRM model as the primary analysis for subjects enriched by baseline PET SUVR between e.g. 1.2 and 1.6 on the FAS.

The rate of change over time (mean slope) based on change from baseline in the CDR-SB will be analyzed using linear mixed effects (LME) models for multivariate normal data derived from a random coefficient model (slope analysis), where the mean slope in each group depends on a continuous assessment time. The LME model will include treatment group, baseline CDR-SB, randomization stratification variables, assessment time, baseline CDR-SB-by-assessment time, and treatment group-by-assessment time. ApoE4 status may be included in the model if appropriate.

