Time to worsening of CDR scores by 24 months will be analyzed on the FAS using Cox regression model for treatment effect adjusting for randomization stratification factors. ApoE4 status may be included in the model if appropriate. (revised per Amendment 05) Time to worsening of a CDR score is defined as time from randomization to worsening of the CDR score (ie, the first worsening in 2 consecutive scheduled visits). For subjects whose CDR scores have not worsened by the end of the Treatment Period of the Core Study, the time to worsening of the CDR score will be censored at the date of last CDR assessment for these subjects.

Time to conversion to dementia for subjects who were not clinically staged as dementia at Baseline based on clinical diagnosis will be analyzed on the FAS using Cox regression model for treatment effect adjusting for randomization stratification factors. ApoE4 status may be included in the model if appropriate. (revised per Amendment 05) Proportion of subjects with dementia diagnosis at 24 months will be estimated using Kaplan—Meier method based on time to conversion to dementia based on clinical diagnosis. Time to conversion to dementia for subjects who were not clinically staged as dementia at Baseline based on clinical diagnosis is defined as time from randomization to conversion to dementia based on clinical diagnosis. For subjects without clinical dementia by the end of study, the time to conversion to dementia based on clinical diagnosis will be censored at the date of last dementia diagnosis.

The other continuous secondary efficacy endpoints as defined above will be analyzed using the same MMRM model as the primary efficacy analysis to compare elenbecestat 50 mg per day versus placebo on the FAS, using baseline value corresponding to the response variable in the model.

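### The Cox models for CDR worsening and conversion to dementia leave out baseline CDR-SB, a valid choice that loses power if that score is prognostic

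*Protocol*

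**What the plan says.** The current text (Amendment 05) of Protocol Section 9.7.1.6.2 describes both time-to-event analyses in the same words: each is "analyzed on the FAS using Cox regression model for treatment effect adjusting for randomization stratification factors". One addition is named: "ApoE4 status may be included in the model if appropriate". The stratification factors, listed in Section 9.7.1.6.1, are "region [7 levels], clinical dementia [yes, no], and concurrent AD medication use at randomization". None of them is baseline CDR-SB.

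The CDR-SB models are built differently:

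- Primary MMRM (Section 9.7.1.6.1): "The MMRM model will include fixed effects of treatment group, visit, treatment group by visit interaction, baseline CDR-SB, baseline CDR-SB by visit interaction", plus the stratification variables.
- ANCOVA after multiple imputation (Section 9.7.1.6.1): baseline CDR-SB is the covariate.
- Slope model (Section 9.7.1.6.2): "The LME model will include treatment group, baseline CDR-SB, randomization stratification variables, assessment time, baseline CDR-SB-by-assessment time" and the treatment-by-time term.

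Section 9.7.1.2 admits a subject to the Full Analysis Set only if they "have baseline and at least 1 postdose primary efficacy measurement", so baseline CDR-SB exists for everyone in either Cox model. The conversion endpoint is confined by definition: "Time to conversion to dementia by 24 months for subjects who were not clinically staged as dementia at Baseline" (Section 9.7.1.1.2).

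**The concern.** Both events are threshold crossings. Section 9.3.1 requires a global CDR of 0.5 at Screening, and Section 9.7.1.1.2 gives as its example of worsening a rise of at least 0.5 on that scale, seen at two consecutive visits. At entry the global score therefore barely separates subjects. The sum of boxes comes from the same six domain ratings (Section 9.2.1) and does show who is already close to the threshold. It is reasonable to expect baseline CDR-SB to predict both events.

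In the worsening model, the yes/no dementia factor is a coarse stand-in for severity. In the conversion model it is essentially constant, because subjects staged as having dementia are excluded.

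The hazard ratio is non-collapsible. If the hazard is λ₀(t)·exp(βA + γX), with A for treatment and X for baseline severity, and X is left out, high-X subjects leave the risk set faster in the arm with the higher hazard. The arms then differ in X among those still at risk, and the estimated treatment hazard ratio moves toward 1 even though randomization balanced X at the start. What is at stake is the size of the reported effect and the power of two secondary endpoints, each tied to a superiority objective in Section 8.2.

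**Working it through.** **1. The plan's own figure.** Section 9.7.2 gives a placebo mean change of 1.46, a 25% reduction, SD 2.05, two-sided alpha 0.05, 90% power and 30% dropout.

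- Difference: 0.25 × 1.46 = 0.365.
- Evaluable per arm: 2 × (1.960 + 1.282)² × 2.05² / 0.365² = 663.
- With dropout: 663 / 0.70 = 948 per arm, or 1896 in total, against 1900 stated. The t-test version gives 1897.

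The stated size reproduces. It concerns CDR-SB only; the protocol gives no event count, hazard ratio or power for either Cox endpoint.

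**2. Inputs for the Cox comparison.**

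- From the protocol: 1900 subjects (Section 9.7.2), about 1:1 allocation, 24 months, 30% dropout. For conversion, about 75% of 1900 = 1425 (1424 simulated), taking the cap of about 25% with mild dementia in Section 9.1 as reached.
- Assumed, not in the protocol: conditional treatment hazard ratio 0.75; placebo event proportion at 24 months of 25% or 50%; baseline CDR-SB standardized, with a prognostic hazard ratio per SD of exp(0.2) = 1.22, exp(0.5) = 1.65 or exp(0.8) = 2.23.

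**3. Simulation.** Exponential event times and exponential dropout were used, with 600 replicates per scenario. Each replicate was fitted by partial likelihood with treatment alone and with treatment plus the covariate. Each pair shows the result without / with baseline CDR-SB.

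| Endpoint (N) | Placebo events | Prognostic HR per SD | Estimated HR | Power, % | Gain, points |
|---|---|---|---|---|---|
| Worsening (1900) | 25% | 1.22 | 0.749 / 0.747 | 78.2 / 78.0 | −0.2 |
| | | 1.65 | 0.758 / 0.753 | 75.2 / 77.0 | 1.8 |
| | | 2.23 | 0.774 / 0.759 | 66.7 / 74.2 | 7.5 |
| | 50% | 1.22 | 0.754 / 0.751 | 97.2 / 96.5 | −0.7 |
| | | 1.65 | 0.763 / 0.750 | 96.2 / 97.7 | 1.5 |
| | | 2.23 | 0.783 / 0.751 | 90.8 / 98.2 | 7.4 |
| Conversion (1424) | 25% | 1.22 | 0.752 / 0.752 | 64.2 / 64.0 | −0.2 |
| | | 1.65 | 0.758 / 0.752 | 61.0 / 63.2 | 2.2 |
| | | 2.23 | 0.768 / 0.749 | 56.8 / 64.8 | 8.0 |
| | 50% | 1.22 | 0.747 / 0.745 | 92.5 / 92.3 | −0.2 |
| | | 1.65 | 0.770 / 0.754 | 85.0 / 89.5 | 4.5 |
| | | 2.23 | 0.784 / 0.751 | 82.0 / 92.7 | 10.7 |

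Monte Carlo error on a single power figure is at most √(0.5 × 0.5 / 600) ≈ 2 points. As a check, Schoenfeld's formula gives 77.7% for 359 events at hazard ratio 0.75, against 78.2% simulated in the first row.

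**4. What the simulation leaves out.** The stratification factors are not modelled, so any prognostic variation that they absorb would shrink the gain. This applies most to worsening, where dementia stage still varies. Events are timed continuously and worsening is not confirmed at a second visit. A smaller simulation of conversion alone (712 per arm, quarterly detection, 40% placebo conversion, 250 trials per scenario) gave power of 80 against 82%, 76 against 81% and 73 against 83% for log hazard ratios of 0.4, 0.6 and 0.8 per SD, so quarterly staging does not change the picture.

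**The case against.** The strongest reply is that nothing here is wrong. A Cox model adjusted for the randomization factors is standard. A reader might infer from the movement toward 1 that the planned hazard ratio is biased or the test invalid, and the documents do not support that. The planned ratio is a less conditional quantity that is valid in its own right, and under the null there is nothing to attenuate. This objection stands, and it limits the point to efficiency.

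Second, for the other continuous secondary endpoints the plan adjusts for the baseline of the response itself. For these two endpoints that baseline is global CDR or dementia stage, which hardly varies at entry. That explains how the omission could arise, but it also supports using CDR-SB, which does vary.

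Third, the size is assumed. The protocol does not say how prognostic baseline CDR-SB is, and entry limits (MMSE of at least 24, global CDR 0.5) narrow its range. The weak-covariate rows show no gain. This stands too: a loss near 10 points should not be read as the expected figure.

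Fourth, it would go too far to say that the conversion model keeps nothing related to severity. AD-medication use remains and may partly reflect it. What is missing is a direct measure.

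Fifth, covariate lists are often completed in the SAP. Here, though, the protocol sets out the list and names one optional addition, so the point concerns a stated choice.

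**Conclusion.** The point holds as a loss of efficiency. Both Cox models omit a baseline score that every analysed subject has and that the MMRM, the multiple-imputation ANCOVA and the slope model use. In the conversion model no direct measure of baseline severity is left.

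If baseline CDR-SB is prognostic, a conditional hazard ratio of 0.75 is estimated at up to about 0.78. The power loss is about nil at a prognostic hazard ratio of 1.22 per SD, about 2 to 5 points at 1.65 and about 7 to 11 points at 2.23. These sizes rest on the assumed treatment effect, event proportions and prognostic strengths, and on leaving out the stratification factors. The direction does not depend on those values; the magnitude does.

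A reader might also infer that the trial's main conclusion is exposed. It is not. Section 9.7.1.1.2 lists both endpoints as other secondary, and the sequential test in Section 9.7.1.6.2 covers only the key secondary endpoints. Nor does the argument carry over to the exploratory analysis of time to change of AD treatment in Section 9.7.1.6.3: nothing in the protocol or in these calculations bears on how baseline CDR-SB predicts that event.

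**What to change.** In Section 9.7.1.6.2, or in the SAP before unblinding, add Visit 2 CDR-SB as a continuous, prespecified covariate to the Cox models for time to CDR worsening and time to conversion to dementia, alongside the stratification factors. State that the reported hazard ratio is then conditional on baseline CDR-SB. The exploratory model for change of AD treatment can stay as it is.

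The cost is one phrase in each model description, with no new data, visits or subjects. If the covariate proves weak, almost nothing is lost. Prespecification matters because adding a covariate after unblinding would not be credible.

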Day	1	15	29	57	85	183	274	365	456	547	638	729		757	813	
Week	1	3	5	9	13	27	40	53	66	79	92	105		109	117	
Weeks elapsed since 1st dose	0	2	4	8	12	26	39	52	65	78	91	104		108	116	
Nominal months elapsed since 1st dose	0		1	2	3	6	9	12	15	18	21	24		25	27	
Procedures/ Assessments																

- b: Subjects who discontinue taking study drug prematurely for any reason will undergo an ED Visit within 7 days of their last dose of study drug. In addition, Follow-up Visits will be scheduled 4 and 12 weeks after the last dose of study drug (Visit 14 and Visit 15, respectively). Subjects who discontinue study drug before reaching 12 months of treatment will also be asked to return to the clinic for a 12 month clinical assessment and then again at 24 months. Subjects who discontinue treatment between 12 and 24 months of treatment will be asked to return to the clinic for a 24 month clinical assessment. Subjects who discontinue early from study drug are considered “on study” as long as they continue to return for their clinical assessments at 12 and 24 months as outlined above, at which efficacy (MMSE, CDR, ADAS- cog14) and quality of life (EQ-5D, QOL-AD and Zarit’s Burden Interview) will be assessed along with concomitant medications. New AEs will be collected for 4 weeks post last dose and followed-up for 12 weeks, or until resolution, whichever comes first. If >4 weeks post last dose only AEs relating to study procedures will be collected. These 12 and 24 month clinical assessment visits do not need to be attended if they fall within 8 days (visit window) after the ED Visit or within ±8 days of either of the Follow-up Visits (Visit 14 and Visit 15).

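### Time to CDR worsening: a worsening first seen at the Month 24 return visit cannot be confirmed for most subjects who stop drug early, and the plan censors it as event-free

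*Protocol*

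**What the plan says.** Three parts of the Protocol (Amendment 05 text) fix this endpoint.

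- **Event.** Section 9.7.1.1.2 gives, as an example, an "increase from baseline by at least 0.5 points on the global CDR scale on 2 consecutive scheduled visits at which global CDR is undertaken". Section 9.7.1.6.2 turns the two-visit requirement into the definition: "worsening of the CDR score (ie, the first worsening in 2 consecutive scheduled visits").
- **Censoring.** If no such worsening has occurred when the Core Study's Treatment Period closes, Section 9.7.1.6.2 says that the time "will be censored at the date of last CDR assessment for these subjects".
- **Visits.** Table 5 schedules post-baseline CDR at Weeks 12, 26, 39, 52, 65, 78, 91 and 104, at the ED Visit, and at Visits 14 and 15. For a subject who completes treatment, Visits 14 and 15 fall at Weeks 108 and 116. For a subject who stops early, footnote b ties them to the last dose: "Follow-up Visits will be scheduled 4 and 12 weeks after the last dose of study drug (Visit 14 and Visit 15, respectively"). After that, a subject who stopped before Month 12 is asked back at Months 12 and 24. One who stopped later "will be asked to return to the clinic for a 24 month clinical assessment". CDR is among the assessments at those return visits.

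No passage says how to treat a worsening first seen at a subject's last CDR, or whether Visits 14 and 15 may confirm a Month 24 worsening.

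**The concern.** A two-visit rule needs a visit after the one at which worsening is first seen. For most early stoppers the Month 24 return visit is the last CDR. A subject found worse there for the first time has no confirmed event and is censored at that visit as not worsened. The subject therefore adds at-risk time, up to Month 24, during which no event could be registered.

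The return visits keep stoppers' outcomes in the Full Analysis Set, and here part of that information is lost. With equal stopping in the two arms, the cost is lost events. With unequal stopping, the arm that stops more looks better even if the drug does nothing. The Protocol states no expected difference in stopping between arms.

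**Working it through.** **The plan's own figure.** No sizing is given for this endpoint. The only sizing figure, in Section 9.7.2, is for the primary endpoint and reproduces. The difference is 0.25 × 1.46 = 0.365, with SD 2.05, two-sided alpha 0.05 and power 90%. That gives 663 evaluable per arm, and 663 / 0.70 rounds up to 948, against 950 stated. The 30% dropout therefore stands for subjects who contribute no Month 24 value, which matters for the size below.

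**Step 1: the CDR calendar.** The ED Visit is taken at the week of last dose, Visits 14 and 15 at +4 and +12 weeks, and visits are consecutive within the subject's own schedule. Where the final CDR is at Week 104, the unconfirmable gap is 104 minus the week of the preceding CDR.

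| Last dose (week) | CDR weeks from last dose on | Unconfirmable gap (weeks) |
|---|---|---|
| 13 | 13, 17, 25, 52, 104 | 104 − 52 = 52 |
| 26 | 26, 30, 38, 52, 104 | 104 − 52 = 52 |
| 52 | 52, 56, 64, 104 | 104 − 64 = 40 |
| 65 | 65, 69, 77, 104 | 104 − 77 = 27 |
| 78 | 78, 82, 90, 104 | 104 − 90 = 14 |
| 85 | 85, 89, 97, 104 | 104 − 97 = 7 |
| 95 | 95, 99, 104, 107 | 0 (Week 107 can confirm) |
| Completer | 104, 108, 116 | 0; or 104 − 91 = 13 if Visits 14 and 15 may not confirm |

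The 8-day skip rule in footnote b moves these by a week or so at some stop times. For a last dose at Week 39, Visit 15 at Week 51 can replace the Month 12 visit, and the gap is 53. Visit 15 falls after Week 104 only if the last dose is after Week 104 − 12 = 92. With stop times uniform over 104 weeks, that is 12/104 = 11.5% of stoppers.

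A worsening already present at the visit before Month 24 is confirmed at Month 24. Only one first seen at Month 24 is lost.

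**Step 2: share of events lost.** Assumptions not in the documents: uniform stop times, every stopper returns, constant hazard, worsening never reverts. The mean gap over stoppers is about 33 of 104 weeks, so evenly spread worsenings would lose 33/104 = 32%. A constant hazard puts more events early. Simulation with 20%, 35% and 50% truly worsened by Month 24 captured about 71%, 71% and 75% of stoppers' events, a loss of 25 to 29%. With 30% stopping and a loss of 27%, 0.30 × 0.27 = 8% of all events are lost.

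**Step 3: effect on the arm comparison, no drug effect.** If stopping proportions are a and b, the ratio of confirmed events is about (1 − 0.27a) / (1 − 0.27b).

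- 40% v 20%: 0.892 / 0.946 = 0.94
- 35% v 25%: 0.9055 / 0.9325 = 0.97

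Simulated ratios of confirmed proportions at 40% v 20% were 0.93 to 0.96. Simulated hazard ratios at 40% v 20%, with 40% worsened by Month 24, were about 0.91 to 0.97. That range covers both readings of Visits 14 and 15, and all or half of the stoppers returning. They were about 0.99 to 1.04 when Month 24 worsenings were counted or when subjects were censored at the last confirmable CDR.

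**The case against.** Several points on the other side are sound and limit the conclusion.

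- **Completers may lose events too.** The endpoint is worsening by 24 months, and the censoring sentence refers to the end of the Treatment Period. Table 5 places Visits 14 and 15 in Follow-Up. If they may not confirm, completers lose any worsening first seen at Week 104. With 30% worsened and 30% stopping, the discarded worsenings were about 2.5% of all subjects among stoppers and 2.3% among completers. Per head that is 2.5/30 = 8.3% of stoppers against 2.3/70 = 3.3% of completers. A reader might infer that only stoppers lose events; the text does not settle that. The imbalance survives on either reading.
- **Late stoppers have a later CDR.** A reader might infer that nobody who stops early is seen after Month 24. That is wrong for last doses after about Week 92.
- **The 30% is not a return rate.** A subject with no Month 24 CDR has no Month 24 worsening to discard. With half returning, the stoppers' discarded worsenings fell from 2.5% to 1.2% of subjects, and one simulated hazard ratio at 40% v 20% was about 0.97.
- **Stakes.** Amendment 05 lists this among the other secondary endpoints, outside the sequential testing of key secondaries.
- **Statistical analysis plan territory.** Section 9.7.1.1.2 words the definition only as an example, and a last-visit rule could be added there. This stands only in part: Section 9.7.1.6.2 itself fixes the event and the censoring date, and applied as written they give the wrong result.
- **Counting every last-visit worsening is not a clean cure.** Completers' last Core Study CDR is Visit 15, so such a rule would admit single-visit Month 27 events. With an assumed 5 to 10% chance of transient worsening per visit, counting unconfirmed worsenings gave hazard ratios of about 1.01 to 1.04 at 40% v 20%, leaning the other way in several scenarios.

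**Conclusion.** The point holds in limited form. The confirmation rule, the censoring date and the visit schedule do not fit together for subjects whose last dose is before about Week 92: a first worsening recorded at Month 24 becomes a censored, event-free observation. The calendar gaps follow from the Protocol alone. The size does not: the share of events lost and the hazard ratios rest on assumed stop times, worsening rates, return rates and stopping imbalance. The bias is modest, at about 0.91 to 0.97 under no effect at an assumed 40% v 20%, and arises only if stopping differs by arm. A reader might infer that the trial's main conclusions are at risk. The documents do not support that, because neither the primary analysis nor the key secondary sequence uses this endpoint.

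**What to change.** Amend Section 9.7.1.6.2, or settle it in the statistical analysis plan before unblinding:

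1. State that a worsening first seen at or before Month 24 may be confirmed at Visit 14 or 15.
2. In both arms, censor subjects without a confirmed event at the last CDR, at or before Month 24, that a later scheduled CDR could have confirmed, instead of at the last CDR. A subject whose last two CDRs are at Weeks 52 and 104 is then censored at Week 52.
3. As a sensitivity analysis, count an unconfirmed worsening at the Month 24 assessment (not Visit 15) as an event in both arms when no later CDR exists.

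No new visits are needed. The main analysis loses a little person-time, and the sensitivity analysis will count some single-visit worsenings that might have reverted.
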